17.2 Quality Assurance

To ensure compliance with ICH-GCP guidelines and all applicable regulatory requirements, Pharmacosmos A/S or its designee may conduct a quality assurance audit following intimation and appointment. Regulatory agencies may also conduct a regulatory inspection of this trial. Such audits/inspections can occur at any time during or after completion of the trial.

17.3 Protocol Deviations

Deviations from the protocol will be registered as protocol deviations which will be classified as minor, major, or GCP deviations.

Out of visit windows will be registered as minor deviations if they are < 30 days.

The following will be assessed as major protocol deviation:

Trial ID: P-Monofer-IDA/CKD-EXT-01

Protocol Version: 2.0 (amendment 1)

Date of Document : 14 June 2017

- Out of visit window of ≥ 30 days after the final visit (i.e. ≥ 212 days after baseline)
- Intake of prohibited medication
- Treatment compliance outside the 80-120 % range
- Other protocol deviations which are assessed as having a clinically or statistically significant effect

18 TRIAL ADMINISTRATION

Pharmacosmos A/S will be responsible for trial administration as described in this section.

A list of laboratories, Contract Research Organizations (CROs), and other vendors will be kept in the trial master file.

18.1 Trial Core Team, GCP Quality Steering Committee, and GCP Quality Board

A Trial Core Team (TCT) will be established for the trial consisting of the following Sponsor personnel:

- Chief medical officer
- Global trial management
- Global medical monitoring
- QC/Regulatory
- BMW

The purpose of the TCT is to ensure high quality, regulatory compliance, scientific validity, and transparency in all activities of the trial via robust planning and timely action. Regular meeting will be held on a monthly basis.

Issues which have a general impact on GCP will be escalated to the GCP Quality Steering Committee consisting of:

- Chief medical officer
- Quality Assurance
- Head of Clinical Trial Management
- Head of Drug Safety
- QC/Regulatory
- BMW

Serious GCP breach and GCP related issues of broad impact to Pharmacosmos A/S could be escalated to the GCP Quality Board consisting of:

- Chief medical officer
- Quality and Regulatory Affairs
- Medical Affairs
- Pharmacosmos CEO

18.2 Direct Access

Direct access to all source data and documents will be mandatory for representatives from Pharmacosmos A/S, Contract Research Organizations, IRB/IEC, Competent Authorities, and other national authorities (e.g. Data Protection Agency) for the purpose of verification of available data.

If an audit or inspection occurs, the PI and institution agree to allow the auditor/inspector direct access to all relevant documents and to allocate his/her time and the time of his/her staff to the auditor/inspector to discuss findings and any relevant issues.

18.3 Trial and Site Closure

Upon completion or premature discontinuation of the site or trial, the CRA will conduct site closure activities with the PI or site staff, as appropriate, in accordance with applicable regulations, ICH-GCP guidelines, and Pharmacosmos A/S or its designee's procedures.

18.4 Records Retention

Following closure of the trial, the PI must maintain all site trial records in a safe and secure location mutually agreeable to the PI, Pharmacosmos A/S or its designee. The records must be maintained to allow easy and timely retrieval when needed (e.g. audit or inspection) and, whenever feasible, to allow any subsequent review of data in conjunction with assessment of the facility, supporting systems, and staff. Where permitted by local laws/regulations or institutional policy, some or all of these records can be maintained in a format other than hard copy (e.g. microfiche, scanned, and electronic); however, caution needs to be exercised before such action is taken. The PI must assure that all reproductions are legible and are a true and accurate copy of the original and meet accessibility and retrieval standards, including re-generating a hard copy, if required. Furthermore, the PI must ensure there is an acceptable back-up of these reproductions and that an acceptable quality control process exists for making these reproductions.

Pharmacosmos A/S or its designee will inform the PI of the time period for retaining these records to comply with all applicable regulatory requirements. The minimum retention time will meet the strictest standard applicable to that site for the trial, as dictated by any institutional requirements, local laws or regulations, or Pharmacosmos A/S or its designee standard procedures; otherwise the retention period will by default be 15 years.

The PI must notify Pharmacosmos A/S or its designee of any changes in the archival arrangements, including, but not limited to, the following: archival at an off-site facility and transfer of ownership of the records if the PI leaves the site.

18.5 Provision of Trial Results and Information to Principal Investigators

When the CSR is completed, Pharmacosmos A/S or its designee will provide the PI with a summary of the trial results. The PI is encouraged to share the summary results with the subjects, as appropriate. In addition, the PI will be given reasonable access to review the relevant statistical tables, figures, and reports and will be able to review the results for the entire trial at a Pharmacosmos A/S site or other mutually agreeable location.

18.6 Finance and Insurance

All agreements between the PI and Pharmacosmos A/S or designee must be signed prior to screening of the first subject in the clinical trial. The agreement must clearly state the rights and obligations of the parties concerned and include a detailed financial settlement.

Every subject participating in the trial will be insured in accordance with the local legal requirements against trial related injuries to health, which may occur during the trial.

Excluded from this, however, are injuries to health and deteriorations of illnesses already in existence which would have occurred or continued to exist even if the subject had not taken part in the clinical trial.

The insurance cover is jeopardised if the subject fails to report immediately to the PI or responsible physician any injury to health, which might have resulted from participation in the clinical trial, or if the subject undergoes any other medical treatment without their consent before the clinical trial has been completely finished, insofar as the individual subject is concerned.

The subject insurance will be arranged by Pharmacosmos A/S on the basis of the final trial protocol.

19 ETHICAL CONSIDERATIONS

19.1 Regulatory and Ethical Considerations

Pharmacosmos A/S or its designee will obtain favourable opinion/approval to conduct the trial from the IRB/IEC, Competent Authorities, and the Data Protection Agency in accordance with the local requirements prior to initiating the trial.

The trial will be conducted in accordance with all applicable regulatory requirements. The trial will also be conducted in accordance with ICH-GCP guidelines, all applicable subject privacy requirements, and the guiding principles of the Declaration of Helsinki.

19.2 Changes to the Protocol

The clinical trial procedures may be changed, and if the changes are substantial, both the IRB/IEC and Competent Authorities, as applicable, must approve/acknowledge the changes before they can be implemented. All substantial changes must be documented by protocol amendments, if applicable.

20 PUBLICATION PLAN

A CSR will be prepared by Pharmacosmos A/S or its designee and reviewed by Pharmacosmos A/S. The CSR or a summary of the CSR should be sent to the IRB/IEC and Competent Authorities according to local legislation.

No data from the clinical trial may be published, presented, or communicated, except to Competent Authorities, prior to the release of the CSR, unless approved by Pharmacosmos A/S in writing. The PIs agree not to discuss externally or publish any result from the trial without the possibility of Pharmacosmos A/S to give comments for up to 90 days after receipt of the manuscript.

The trial will be registered at Clinicaltrials.gov.

The results of the trial, positive as well as negative, will be published by the end of the trial.

If the results of the trial are to be published in a journal, the authorship credit should be based on (1) substantial contributions to conception and design, acquisition of data, or analysis and interpretation of data; (2) drafting the article or revising it critically for important intellectual content; (3) final approval of the version to be published. Authors should meet conditions 1, 2, and 3.

20.1 Uploading of Data on Public Websites

The primary endpoint and key secondary endpoints will be uploaded on public websites in according to national requirements. Key secondary endpoints in the trial are the following:

- Change in Hb from baseline to week 2 and months 3 and 6
- Change in *s*-ferritin and TSAT from baseline to week 2 and months 3 and 6

APPENDIX A

Standardised MedDra query (SMQ) terms (including four additional terms) for definition of hypersensitivity events

Group A: Narrow terms pertaining to hypersensitivity reactions

- Anaphylactic reaction
- Anaphylactic shock
- Anaphylactic transfusion reaction
- Anaphylactoid reaction
- Anaphylactoid shock
- Circulatory collapse
- First use syndrome
- Kounis syndrome
- Shock
- Type I hypersensitivity

Group B: Broad terms pertaining to respiratory reactions potentially related to hypersensitivity

- Acute respiratory failure
- Asthma
- Bronchial oedema
- Bronchospasm
- Cardio-respiratory distress
- Chest discomfort
- Choking
- Choking sensation
- Circumoral oedema
- Cough
- Cyanosis
- Dyspnoea
- Hyperventilation
- Laryngeal dyspnoea
- Laryngeal oedema
- Laryngospasm
- Laryngotracheal oedema
- Mouth swelling
- Nasal obstruction
- Oedema mouth

- Oropharyngeal spasm
- Oropharyngeal swelling
- Respiratory arrest
- Respiratory distress
- Respiratory failure
- Reversible airways obstruction
- Sensation of foreign body
- Sneezing
- Stridor
- Swollen tongue
- Tachypnoea
- Throat tightness
- Throat oedema
- Tracheal obstruction
- Tracheal oedema
- Upper airway obstruction
- Wheezing

Group C: Broad terms pertaining to skin reactions potentially related to hypersensitivity

- Allergic oedema
- Angioedema
- Erythema
- Eye oedema
- Eye pruritus
- Eye swelling
- Eyelid oedema
- Face oedema
- Flushing
- Generalised erythema
- Injection site urticaria
- Lip oedema
- Lip swelling
- Ocular hyperaemia
- Oedema
- Periobital oedema
- Pruritus
- Pruritus allergic

Trial ID: P-Monofer-IDA/CKD-EXT-01

Protocol Version: 2.0 (amendment 1)

Date of Document : 14 June 2017

- Pruritus generalised
- Rash
- Rash erythematous
- Rash generalised
- Rash pruritic
- Skin swelling
- Swelling
- Swelling face
- Urticaria
- Urticaria papular

Group D: Broad terms pertaining to cardiovascular reaction potentially related to hypersensitivity

- Blood pressure decreased
- Blood pressure diastolic decreased
- Blood pressure systolic decreased
- Cardiac arrest
- Cardio-respiratory arrest
- Cardiovascular insufficiency
- Diastolic hypotension
- Hypotension

Group E: Additional terms defined by the Food and Drug Administration (FDA)

- Syncope
- Unresponsiveness
- Loss of consciousness
- Seizure

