5.2 Secondary Safety Endpoints

The secondary safety endpoints are the following:

- Serious or severe hypersensitivity reaction starting on or after the treatment with iron isomaltoside (i.e. treatment-emergent). The hypersensitivity terms are defined as standardised Medical Dictionary for Regulatory Activities query (SMQ) terms (including four additional terms) in Appendix A.
- Composite cardiovascular adverse events (AEs) starting on or after the treatment with iron isomaltoside (i.e. treatment-emergent). The adjudicated composite AEs includes the following:
 - Death due to any cause
 - Non-fatal myocardial infarction
 - Non-fatal stroke
 - Unstable angina requiring hospitalization
 - Congestive heart failure requiring hospitalization or medical intervention
 - Arrhythmias
 - Hypertension
 - Hypotension

The AEs will be adjudicated by an independent clinical events classification committee (described in a separate adjudication charter). The specified definition of adjudicated endpoints is given in Appendix B.

- Time to first composite cardiovascular safety AE
- Serum (*s*-) phosphate < 2 mg/dL at any time from baseline to month 6

In addition, physical examinations and measurements of vital signs, height, weight, electrocardiogram (ECG), and safety laboratory parameters will be measured as part of standard safety assessments.

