12.4 Collection of Adverse Events

The Investigator is responsible for ensuring that all AEs (as defined in Section 12.1) observed by the Investigator or reported by the subject are properly collected and recorded in the subject’s medical record as well as in the AE pages of the eCRF.

Screen failures: All SAEs will be reported in the eCRF from the time a subject has signed the ICF and until he/she exits the trial. Non-serious AEs occurring in subjects who are never treated with the trial drug will not be collected.

Treated subjects: From the time a subject has signed the ICF and until he/she exits the trial, all AEs/SAEs will be reported in the eCRF. AEs/SAEs occurring before administration of the trial drug are considered as non-treatment emergent, and those occurring after administration of the trial drug are considered as treatment emergent.

If a subject is permanently withdrawn from the trial because of an AE, this information must be included in the final visit form.

An AE should be described in the following manner: The nature of the event will be described in precise, standard medical terminology (i.e. not necessarily the exact words used by the subject). If known, a specific diagnosis should be stated. Furthermore, the Investigator should describe an AE regarding seriousness (see Section 12.2), severity, relatedness, action taken, and outcome.

Severity

- Mild: The AE does not interfere in a significant manner with the subject's normal functioning level, but may be an annoyance
- Moderate: The AE produces some impairment of functioning but is not hazardous to health, but is uncomfortable and/or an embarrassment
- Severe: The AE produces significant impairment of functioning or incapacitation and is a hazard to the subject

Relatedness

- Related: The AE is related to the medicinal product
- Possible related: A causal relationship is conceivable and cannot be dismissed
- Unlikely related: The event is most likely related to an aetiology other than the medicinal product
- Not related: No relatedness to the medicinal product

The categories "related" and "possible related" will be classified as related AEs and the categories "unlikely related" and "not related" will be classified as unrelated AEs in the clinical study report (CSR).

Outcome

- Recovered/resolved: Complete clinical recovery without any sequel attributable to the event as per Investigator's discretion

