7.2 Secondary Safety Endpoints

The secondary safety endpoints are the following:

- Serious or severe hypersensitivity reaction starting on or after the treatment with iron isomaltoside (i.e. treatment-emergent). The hypersensitivity terms are defined as standardised Medical Dictionary for Regulatory Activities query (SMQ) terms (including four additional terms) in protocol Appendix A.
- Composite cardiovascular AEs starting on or after the treatment with iron isomaltoside (i.e. treatment-emergent). The adjudicated composite AEs includes the following:
 - Death due to any cause
 - Non-fatal myocardial infarction
 - Non-fatal stroke
 - Unstable angina requiring hospitalization
 - Congestive heart failure requiring hospitalization or medical intervention
 - Arrhythmias
 - Hypertension
 - Hypotension
- Time to first composite cardiovascular safety AE
- Serum (s-) phosphate < 2 mg/dL at any time from baseline to month 6

Additional safety assessments are physical examinations and measurements of vital signs, height, weight, electrocardiogram (ECG), and safety laboratory parameters.

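### Appendix A omits unqualified hypersensitivity, drug hypersensitivity and infusion related reaction, so a serious or severe event coded only to one of these falls outside the hypersensitivity endpoint

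*Protocol*

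**What the plan says.** Protocol 5.2 lists serious or severe treatment-emergent hypersensitivity first among the secondary safety endpoints and says how events are recognised: "The hypersensitivity terms are defined as standardised Medical Dictionary for Regulatory Activities query (SMQ) terms (including four additional terms) in Appendix A". SAP 7.2 repeats the definition, points to the same appendix and adds no terms.

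Appendix A has five groups. The first is headed "Group A: Narrow terms pertaining to hypersensitivity reactions". Groups B to D hold broad respiratory, skin and cardiovascular terms, and Group E adds four terms attributed to the FDA.

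Events are coded in MedDRA (Protocol 15.6, SAP 7.3.1). SAP 7.3.1 plans two tables, one of serious or severe hypersensitivity reactions and one of hypersensitivity reactions of any severity, with a listing for each. On recording, Protocol 12.4 asks for precise medical terminology and adds: "If known, a specific diagnosis should be stated".

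**The concern.** The endpoint is named for hypersensitivity reactions, yet an event coded simply as hypersensitivity matches nothing on the list that defines it. Two sites could see the same reaction. One records wheezing, rash and hypotension and produces a case. The other records a drug hypersensitivity reaction and may not. Capture would then depend partly on wording.

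This matters because the trial's primary objective is safety after re-dosing, and Protocol 10.2 singles out hypersensitivity for observation after each administration. Few such events can be expected to decide the content of these tables in a trial of about 100 subjects, so a single omission would be visible in them.

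**Working it through.** The plan gives no figure to reproduce for this endpoint, so the check is mainly a reading of the list.

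1. **Size of the list.** Groups A to E as printed: 10 + 37 + 28 + 8 + 4 = 87 terms.

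2. **Word search of the 87 terms.** The string hypersens occurs once ("Type I hypersensitivity"), infusion never, and drug never. The string allerg occurs twice (allergic oedema, pruritus allergic). The string anaphyl occurs five times and reaction three times; "Anaphylactic reaction" is among both sets. The only administration-site term is injection site urticaria, although Protocol 10.2 gives the drug as an infusion.

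3. **What happens to each label**, for a serious or severe event after dosing, assuming it is coded to a term of the same wording:

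| Coded term | On the list? |
|---|---|
| Anaphylactic or anaphylactoid reaction or shock | Yes, Group A |
| Type I hypersensitivity | Yes, Group A |
| Dyspnoea, wheezing, bronchospasm | Yes, Group B |
| Angioedema, urticaria, rash | Yes, Group C |
| Hypotension | Yes, Group D |
| Hypersensitivity (unqualified) | No |
| Drug hypersensitivity | No |
| Infusion related reaction | No |
| Infusion site urticaria | No, though urticaria and injection site urticaria are |

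4. **Is there another route in?** Protocol 5.2 attaches adjudication to the cardiovascular composite, and Appendix B defines only cardiovascular endpoints. Neither document describes a medical review that would bring an unlisted term into the hypersensitivity endpoint.

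5. **Where an unlisted event still shows.** It appears in the TEAE tables and, if serious, in the treatment-emergent SAE tables. If judged related or possibly related, it counts in the primary endpoint (ADRs, SAP 7.1) and, if also serious, among SARs (SAP 7.3.1). Exact limits are planned for the number of subjects with ADRs and with SARs.

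6. **Illustrative size.** Inputs: n = 100 (the recruitment target in Protocol 8.1) and one event coded to an unlisted term (assumed). The exact Clopper-Pearson limits for x events are the 0.025 quantile of Beta(x, n - x + 1) and the 0.975 quantile of Beta(x + 1, n - x).
 - x = 0: lower limit 0; upper limit 1 - 0.025^(1/100) = 3.62%.
 - x = 1: lower limit 1 - 0.975^(1/100) = 0.03%; upper limit 5.45%.
 - For comparison, x = 2 gives 0.24 to 7.04%.

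**The case against.** The list is a deliberate choice: standard query terms plus four more. For serious or severe reactions, anaphylactic reaction and similar diagnoses are natural labels, and they are counted. Much of this stands, and it rules out several stronger readings that a reader might infer.

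- *Any reaction reported as a diagnosis is missed, so the clearest cases are lost.* The list contains anaphylactic, anaphylactoid, Type I hypersensitivity, angioedema and urticaria terms. Only events recorded solely under a generic label are at risk.
- *Section 12.4 steers compliant sites into the gap.* It asks for a specific diagnosis when one is known. It does not tell sites to drop symptoms, and a generic label is not clearly the specific diagnosis requested.
- *A missed event disappears.* It stays in the TEAE and, where applicable, SAE, ADR and SAR outputs.
- *One missed case decides the result.* No hypothesis is tested and no interval is planned for this endpoint.
- *The list departs from the standard query.* Neither document reproduces the query, so this cannot be judged.

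The Protocol Summary does say in general terms that events will be adjudicated, under a charter that is not part of these documents. Since Protocol 5.2 and Appendix B confine adjudication to cardiovascular endpoints, this cannot be relied on to rescue a hypersensitivity event, but the charter's content is unknown.

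It is also fair to say that not every infusion reaction is hypersensitivity, and that an open-ended clause admitting any allergic-sounding report would bring judgement into an open-label trial. The fix should avoid both. None of this fills the gap for the generic terms.

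**Conclusion.** The point holds in a limited form. Followed exactly, the plan leaves a serious or severe event coded only as hypersensitivity, drug hypersensitivity or infusion related reaction out of both hypersensitivity tables and both listings. The loss is to this secondary endpoint, not to the trial's safety record.

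The conclusion rests on one assumption that the documents cannot settle: that such a report is coded to a term of like wording. How often this would happen is unknown, because no expected rate is given. The change from 0/100 to 1/100 shows only what a single event would do. This is a cheap improvement, not a flaw that undermines the endpoint.

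**What to change.** In SAP 7.2 and 7.3.1, keep Groups A-E as the defined endpoint. To each hypersensitivity table add a supplementary row, with a matching listing, for Groups A-E plus two named terms: hypersensitivity and drug hypersensitivity. Show infusion related reaction and infusion site urticaria separately, so that they are visible without being counted as hypersensitivity. Fix the terms before database lock and record the addition as a deviation in SAP section 8. Do not add an open-ended category.

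The cost is one supplementary row in each of the two tables, a separate line for the infusion terms, and the extra listing. The supplementary rate may be slightly higher than the A-E rate. The A-E result is unchanged, so comparability with other uses of that list is kept.

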APPENDIX B

Adjudicated composite cardiovascular endpoints

1. Death due to any cause will be adjudicated as the date the subject is pronounced dead.

2. Myocardial infarction: A myocardial infarction (MI) will be defined as the presence of the characteristic changes in cardiac enzyme markers in the setting of either temporally related symptoms of an acute coronary syndrome or electrocardiographic (ECG) changes consistent with either ischemia or infarction.

Cardiac enzyme markers indicative of an MI will include:

- An appropriate rise and fall in serum troponin (I or T) or creatine kinase-MB where at least 1 value is $\geq 2 \times$ upper limit of normal (ULN). Where only 1 value has been measured, if it is $\geq 2 \times$ ULN, an event may be adjudicated based on the totality of the clinical evidence.
- Where only total creatine phosphokinase is measured, serial changes (i.e. at least 2 values) need to be $\geq 2 \times$ ULN.

Symptoms indicative of ischemia will need to have been present for ≥ 10 minutes and may include chest pain, chest pressure, or chest tightness. Dyspnoea, diaphoresis, or nausea may be considered symptoms of ischemia and will be judged based on the totality of the clinical evidence.

ECG changes will be defined as:

- New Q waves in 2 or more contiguous leads
- Evolving ST-segment to T-wave changes in 2 or more contiguous leads + (such as ≥ 0.5 mm transient ST-segment depression)
- New left bundle branch block
- 1 mm ST-segment elevation in 2 or more contiguous leads

3. Stroke: A stroke is defined as a focal neurological deficit of sudden onset that is not reversible within 24 hours that results from a vascular cause involving the central nervous system and is not due to another readily identifiable cause (i.e. brain tumour or trauma). Strokes will be sub-classified as haemorrhagic, ischaemic, or unknown.

4. Unstable angina requiring hospitalization: Unstable angina requiring hospitalization will be defined as ischemic symptoms meeting the following criteria:

1. Lasting ≥ 10 minutes and considered to be myocardial ischemia on final diagnosis
AND
2. Requiring an unscheduled visit to a health care facility and overnight admission (does not include chest pain observation units)
AND
3. At least one of the following:
 - New dynamic ECG changes

- Ischemia evidence on stress testing with or without cardiac imaging
- Angiographic evidence of ≥ 70 % lesion and/or thrombus in an epicardial coronary artery

5. Congestive heart failure requiring hospitalization or medical intervention will meet the following criteria:

1. Requires hospitalization defined as an admission to an inpatient unit or a visit to an emergency department that results in at least a 12-hour stay (or a date change if the time of admission/discharge is not available)

AND

2. Clinical manifestation of congestive heart failure including at least one of the following: new or worsening dyspnoea, orthopnoea, paroxysmal nocturnal dyspnoea, oedema, pulmonary basilar crackles, jugular venous distension, or radiological evidence of worsening heart failure

AND

3. Additional/increased therapy
 - a. Intravenous treatment with diuretic, inotrope, or vasodilator therapyOR
 - b. Mechanical or surgical intervention (mechanical circulatory support, heart transplantation, or ventricular pacing to improve cardiac function) or the use of ultrafiltration, hemofiltration, or dialysis that is specifically directed at treatment of heart failure

6. Arrhythmia will be defined as any symptomatic deviation from normal sinus rhythm experienced by the subject that results in an evaluation by a health care provider. The evaluation may include a physical exam during an outpatient visit, an ECG, or a hospital admission. Arrhythmias may include any conduction abnormality, atrioventricular heart block, prolongation of QTc interval, supraventricular/nodal arrhythmia, vasovagal episode, ventricular arrhythmia, or other cardiovascular arrhythmia.

7. Hypertension

- During the observation period immediately following trial drug administration, hypertension will be defined as an increase in systolic blood pressure > 20 mm Hg that results in a value > 180 mm Hg or an increase in diastolic blood pressure > 15 mm Hg that results in a value > 105 mm Hg
- Following the release of a subject from the trial visit during which they are receiving medication, hypertension will be defined as requiring an unscheduled outpatient health care visit, a hospital admission, or a change in medical therapy (e.g. administration of antihypertensives) in conjunction with the objective criteria, a rise in blood pressure (an increase in systolic blood pressure > 20 mm Hg that results in a value > 180 mm Hg or an increase in diastolic blood pressure > 15 mm Hg that results in a value > 105 mm Hg)

Trial ID: P-Monofer-IDA/CKD-EXT-01

Protocol Version: 2.0 (amendment 1)

Date of Document : 14 June 2017

8. Hypotension

- During the observation period immediately following trial drug administration, hypotension will be defined as a decrease in systolic blood pressure > 20 mm Hg that results in a value < 90 mm Hg or a decrease in diastolic blood pressure > 15 mm Hg that results in a value < 50 mm Hg.
- Following the release of a subject from the trial visit during which they are receiving medication, hypotension will be defined as requiring an unscheduled outpatient health care visit, a hospital admission, or a change in medical therapy (e.g. fluid/volume repletion, holding of antihypertensives) in conjunction with the objective criteria, a decrement in blood pressure (a decrease in systolic blood pressure > 20 mm Hg that results in a value < 90 mm Hg or a decrease in diastolic blood pressure > 15 mm Hg that results in a value < 50 mm Hg).
